5.5 Discontinuation of investigational product and withdrawal from study

Patients **may** be discontinued from investigational product in the following situations:

- Patient decision. The patient is at any time free to withdraw his/her participation in the study, without prejudice
- Adverse events
- Pregnancy
- Severe non-compliance to this protocol as judged by the investigator and/or AstraZeneca
- Confirmed disease progression
- Patients incorrectly initiated on investigational product (Section 5.5.2)
- Patient lost to follow-up

Patients that are withdrawn from the study but are evaluable will not be replaced.

Patients may withdraw from any aspects of the voluntary exploratory research (see Section 5.5.3) at any time, without prejudice to further treatment and independent of any decision concerning participation in other aspects of the main study.

5.5.1 **Procedures for discontinuation of a patient from investigational product**

The Principal Investigator/Investigator will perform the best possible observation(s), test(s) and evaluation(s) as well as give appropriate medication and all possible measures for the safety of the subject. They will also immediately inform AstraZeneca of the withdrawal. Adverse events will be followed up; all unused study drug should be returned by the subject or representative (e.g. caretaker, family member).

If AZD9291 is discontinued for any reason, the patient must complete all assessment at discontinuation visit specified in study plan (Table 2). Study procedure related SAEs and concomitant medication must be captured till 28 day safety follow-up visit.

5.5.2 Procedures for handling patients incorrectly initiated on investigational product

Patients who fail to meet the inclusion/exclusion criteria should not, under any circumstances, be enrolled or receive study medication. There can be no exceptions to this rule.

Where patients that do not meet the inclusion criteria are enrolled in error or incorrectly started on treatment, or where patients subsequently fail to meet the study criteria post initiation, the investigator should inform the AstraZeneca Global Study Team Physician immediately. The decision on when to discontinue the ineligible patient from the study is based on the medical/ safety risk for the patient. The AstraZeneca Global Study Team Physician is to ensure all such contacts are appropriately documented.

5.5.3 Procedures for withdrawal from study

Patients are at any time free to withdraw from the study (investigational product and assessments), without prejudice to further treatment (withdrawal of consent). Such patients will always be asked about the reason(s) and the presence of any adverse events. If possible, they will be seen by an investigator and undergo the assessments and procedures scheduled for the post study assessment (see Section 6.4.3) and inform AstraZeneca of the withdrawal. Adverse events should be followed up (see Sections 6.4.3 and 6.4.4) and study drug should be returned by the patient.

5.6 Study timetable and

Planned duration of the study:

Study period: Q2 2015- Q4 2016

The end of the study is defined as 'the last visit of the last subject undergoing the study', this may be due to all the patients having discontinued treatment due to PD and/or meeting discontinuation criteria and completed 28 days post treatment safety follow-up/withdraw from the study.

6. STUDY PLAN AND COLLECTION OF STUDY VARIABLES

6.1 Study Plan

Table 2Study Plan

Study Plan 40 & 80 mg tablet cohort

	Screening	Sing (7 d	gle dose ay cycl	e /Cycl e)	le O		Mult Cycle	iple I e 1 (2	Dosing/ 1 Day (cycle)	Cycle 2 – Cycle 4 (21 Day Cycle)	Cycle 2 only	Cycle 5 onwards (21 Day cycle)	Discontinuation	28-day Follow-Up	Details in Section
Visit	1	2	3	4	5	5	6	7	8	9	10+					
Day	-28 to -1	D1	D2	D3	D4	D6	D1	D8	D9	D15	D1	D2				
Window (Days)		0	0	0	0	0	0	0	0	0	±7	0	±7	0	±7	
Informed Consent	Х															4
Demography & baseline characteristics	Х															6.3.1
Medical/surgical history	Х															6.3.1
Inclusion/Exclusion Criteria	Х															4
Physical Examination	Х	Х					Х				Х		Х	X		6.3.2
WHO Performance Status	Х	Х					Х				Х		Х	Х		6.3.2
Pregnancy Test (pre- menopausal females only)	X															6.3.5
Ophthalmologic assessment	Х	•	As clinically indicated								6.3.6					
Vital Signs	X	X	Х				X	X	X	X	X	Х	Х	X		6.3.3
Height	X															6.3.3

Weight	Х	Х					Х				Х		Х	X		6.3.3
ClinicalChemistry/Hae matology/Urinalysis	X	X					Х	Х		X	X		X	X		6.3.5
ECG	Х	Х					Х				Х		Х	X		6.3.4
Echo/MUGA	X	-				1	2 week	dy(±1	week)	relativ	ve to first d	ose				6.3.7
PK blood samples (including metabolites)		X	X	X	X	X	X	X	X	X	X (Cycle 2 only)	X				6.5.1
RECIST assessments	X ^(b)						•	Every	y 6 we	eks(±1	week) ^(c)					6.7.1
Dispense Study Medication		X					X				X		X			5
Dose with AZD9291		Х					•	-		Da	aily dosing					5
Concomitant Medication	•			·	·									· · ·	•	4.3.1
Adverse Events ^(d,e)	•														►	6.4

(a) If assessments were performed within 7 days prior to the first dose of study treatment and the patient meets the eligibility criteria, these assessments do not need to be repeated during visit 2.

(b) This assessment does not need to be repeated if it is performed within 28 days prior to the start of study treatment, unless the investigator has a reason to believe that there has been a change in the patient's tumour burden. If imaging is repeated before the start of study treatment, the most recent assessment would then be recorded as the screening tumour assessment.

(c) RECIST assessments should be performed every 6 weeks (\pm 7 days) from visit 6(C1D1).

(d) Following AZD9291 discontinuation, SAEs considered related to study procedures should continue to be collected

(e) Continued to collect unresolved AEs post 28-day Follow-up visit (if applicable).

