AZD9291 is an oral, potent, selective, irreversible inhibitor of both EGFR-TKI sensitising and T790 mutations in NSCLC with a significant selectivity margin over wild-type EGFR. AZD9291 will be administered orally as a tablet once a day. A cycle of treatment is defined as 21 days of once daily AZD9291 treatment.

On clinic days on which PK samples are scheduled to be taken, the dosing should be delayed until arrival at the clinic and until the pre-dose ECG has been performed followed by the pre-dose PK sample. Patients should not take their dose until instructed to do so by site personnel.

Duration of treatment

Patients in both cohorts (40 mg and 80 mg once daily) may continue on treatment with AZD9291 until a treatment discontinuation criterion is met. There is no maximum duration of treatment as patients may continue to receive AZD9291 beyond RECIST 1.1 defined progression as long as they are continuing to receive clinical benefit, as judged by the investigator (see Section 5.2).

Outcomes variable(s)

Primary endpoints/variables

PK exposure parameters derived from plasma concentrations of AZD9291, and metabolites AZ5104 and AZ7550.

Following the single dose part (or first dose) of the study:

Maximum plasma concentration (C_{max}), time to Cmax (t_{max}), terminal rate constant (λz), terminal half life ($t_{\nu_{2}\lambda z}$), area under the plasma concentration-time curve from zero to 24 hours (AUC₍₀₋₂₄₎), from zero to 72 hours (AUC₍₀₋₇₂₎), from zero to the time of the last measurable concentration (AUC_(0-t)) and from zero to infinity (AUC), apparent plasma clearance (CL/F) (AZD9291 only), apparent volume of distribution (AZD9291 only), mean residence time (MRT), where possible.

Following the multiple dose part of the study:

Cycle 2 Day 1

Maximum plasma concentration at steady state ($C_{ss max}$), time to $C_{ss max}$ ($t_{ss max}$), minimum plasma concentration at steady state ($C_{ss min}$), area under the plasma concentration-time curve from zero to the end of the dosing interval (AUCss), apparent plasma clearance at steady state (CL_{ss}/F) (AZD9291 only), extent of accumulation on multiple dosing (R_{AC}), time dependency of the pharmacokinetics where possible.

Cycle 1 Day 8

C_{C1D8 max}, t_{C1D8 max}, C_{C1D8 min}, AUC_{tau}

Trough concentrations on Cycle 1 Day 8, day 15 and Cycle 2 day 1.

The ratio of metabolite to AZD9291 will also be calculated.

Secondary endpoints/variables

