3.1 Overall study design and flow chart

This is a phase I, open-label, two parts (Part A and Part B) study to determine the pharmacokinetics of AZD9291 administered orally at two dose levels (40 mg and 80 mg) in patients with locally advanced or metastatic NSCLC who have progressed following prior therapy with an approved EGFR TKI agent (+/- additional chemotherapy regimens).

Approximately 24 patients will enter into this study, with 12 patients at each dose level

- Cohort 1 will investigate the pharmacokinetics of single then multiple dosing of AZD9291 at 40 mg once daily dose.
- Cohort 2 will investigate the pharmacokinetics of single then multiple dosing of AZD9291 at 80 mg once daily dose.

The enrollment of Cohort 2 will start after Cohort 1 finishes the enrollment. The first 12 patients enrolled in the study will be in 40 mg dose Cohort.

Patients will be administered a single dose of AZD9291 on Day 1, Cycle 0 at the beginning of Part A period. From Day 2 to Day 6, no treatment will be given, but PK samples will be obtained; on Day 8 (Cycle1, Day1), the patients will be administered AZD9291 once daily on a continuous schedule, ie, no break in AZD9291 dosing. Part A will complete after Cycle 4 treatment and Part B will start without treatment interruption.

Patients in both cohorts should continue on treatment with AZD9291 until a treatment discontinuation criterion is met. There is no maximum duration of treatment as patients may continue to receive AZD9291 beyond RECIST 1.1 defined progression as long as they are continuing to receive clinical benefit, as judged by the investigator.

The whole study will be divided nominally into two parts: Part A will assess the pharmacokinetics and preliminary efficacy and safety of AZD9291 at 40 mg and 80 mg respectively, and Part B will assess only the safety and efficacy data of AZD9291.

Following completion of the Part A, patients will automatically continue to Part B.

There are two data cut offs:

- 1. PK and preliminary efficacy and safety data base lock will take place approximately 3 months after LSI and after the part A completes, to allow all patients have two tumor assessments after the first dose.

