5.2 Dose and treatment regimens

AstraZeneca will supply AZD9291 as tablets for oral administration as a single daily dose of 40 mg and 80 mg respectively. At each dispensing visit, sufficient AZD9291 for 21 days treatment, plus overage, will be dispensed.

Patients will be administered a single dose of AZD9291 on Day 1, Cycle 0 at the beginning of Part A period. From Day 2 to Day 6, no treatment will be given, but PK samples will be obtained; on Day 8 (Cycle1, Day1), the patients will be administered AZD9291 on a continuous schedule. Part A treatment will complete at the end of Cycle 4 and treatment in Part B will continue.

Patients may continue receiving AZD9291 until treatment discontinuation criteria are met. Patients may receive AZD 9291 beyond disease progression as long as they are considered to receive clinical benefit continuously judged by the treating physician.

Patients who were started and have remained on treatment at a dose of 40mg for at least 6 months, have shown clinical benefit (as judged by the investigator) and have then developed RECIST confirmed disease progression, and did not experience any treatment – related grade 3 AE when treated at dose of 40mg, may have dose increased to 80mg after agreement in advance between the Investigator and AZ Study Physician. 80mg has been declared to have an acceptable tolerability profile by the Safety Review Committee.

Tablets should be taken whole with water, 240ml being the recommended volume for PK days. AZD9291 can be taken with or without food at the same time each day. Patients will be required to fast (water only) for at least 8 hours prior to the collection of a fasting glucose sample as per the study plan (Table 2).

Doses should be taken approximately 24 hours apart at the same time each day. Doses should not be missed. If a patient misses taking a scheduled dose, within a window of 12 hours, it is acceptable to take the dose. If it is more than 12 hours after the dose time, the missed dose should not be taken, and patients should be instructed to take the next dose at the next scheduled time. If a patient vomits after taking their AZD9291, they should not make up for this dose, but should take the next scheduled dose.

Any change from dosing schedule, dose interruptions, dose reductions should be recorded in the eCRF.

Assessment timings if dosing is interrupted

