7.4 Calculation or derivation of pharmacokinetic variables

Pharmacokinetic analysis of the plasma concentration data for AZD9291 and its metabolites will be performed by Quantitative Clinical Pharmacology, Alderley Park, AstraZeneca or delegate on behalf of Quantitative Clinical Pharmacology. The actual sampling times will be used in the parameter calculations and PK parameters will be derived using standard non-compartmental methods.

Where possible the following PK parameters will be determined for AZD9291, AZ5104 and AZ7550.

Following the single dose part (or first dose) of the study:

Maximum plasma concentration (C_{max}), time to C_{max} (t_{max}), terminal rate constant (λ_z), terminal half life ($t_{\frac{1}{2}\lambda_z}$), area under the plasma concentration-time curve from zero to 24 hours (AUC₍₀₋₂₄₎), from zero to 72 hours (AUC₍₀₋₇₂₎), from zero to the time of the last measurable concentration (AUC_(0-t)) and from zero to infinity (AUC), apparent plasma clearance (CL/F)

(AZD9291 only), apparent volume of distribution, mean residence time (MRT), where possible.

Following the multiple dose part of the study:

Cycle 2 Day 1:

Maximum plasma concentration at steady state ($C_{ss max}$), time to $C_{ss max}$ ($t_{ss max}$), minimum plasma concentration at steady state ($C_{ss min}$), area under the plasma concentration-time curve from zero to the end of the dosing interval (AUC_{ss}), apparent plasma clearance at steady state (CL_{ss}/F) (AZD9291 only), extent of accumulation on multiple dosing (R_{AC}), time dependency of the pharmacokinetics.

Cycle 1 Day 8:

CC1D8 max, tC1D8 max, CC1D8 min, AUCtau.

Trough concentrations on Cycle 1 Day 8, day 15 and Cycle 2 day 1.

The ratio of metabolite to AZD9291 will also be calculated.

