The maximum plasma concentration (C_{max}), the C_{max} at steady state ($C_{ss max}$), the time of maximum concentration (t_{max}) and the t_{max} at steady state ($t_{ss max}$) will be determined by inspection of the concentration-time profiles. Where possible the terminal elimination rate constant (λ_{z}) will be calculated by log-linear regression of the terminal portion of the concentration-time profiles where there are sufficient data and the terminal half-life $(t_{\nu_{\lambda}z})$ will be calculated as $\ln 2/\lambda_z$. The area under the concentration-time curve up to the last quantifiable sample (AUC_(0-t)) and the area under the concentration-time curve up to 24 hours (AUC₍₀₋₂₄₎) will be calculated using the linear up log down trapezoidal rule. Where appropriate, the AUC(0-t) will be extrapolated to infinity using λz to obtain AUC. The area under the concentration-time curve across the dosing interval, AUCss will be calculated using the linear up log down trapezoidal rule. The apparent clearance (CL/F following the single dose and CLss/F following multiple dosing) will be determined from the ratio of dose/AUC or dose/AUCss. The volume of distribution (Vss/F or Vz/F) will be determined from the mean residence time (MRT) x CL/F and/or the accumulation ratio (RAC) will be calculated as the ratio of the AUC(0-24) on Cycle 2 Day 1 and Cycle 0 Day 1. The time dependency of the pharmacokinetics on multiple dosing will be assessed by the calculation of the ratio of AUC(0 -24) Cycle 2 day 1/AUC Cycle 0 Day 1.

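### Table 2 gives the Cycle 2 Day 1 PK profile a ±7-day window while every other PK day has 0, so the steady-state parameters may come from multiple-dosing day 15 to day 29

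*Protocol*

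**What the plan says.** The window row of Table 2 (Protocol, section 6.1) reads "Window (Days) 0 0 0 0 0 0 0 0 0 ±7 0 ±7 0 ±7". The screening cell is blank, so these 14 entries belong to the 14 columns after screening. The PK row places the Cycle 2 Day 1 samples in the column shared by Day 1 of Cycles 2, 3 and 4, marked as applying to Cycle 2 only.

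The nominal day of that profile follows from two statements. Section 3.1 says that "on Day 8 (Cycle1, Day1), the patients will be administered AZD9291 once daily on a continuous schedule". The synopsis says: "A cycle of treatment is defined as 21 days of once daily AZD9291 treatment".

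Section 7.4 assigns to Cycle 2 Day 1 the maximum, time of maximum and minimum at steady state, AUCss and CLss/F, together with "extent of accumulation on multiple dosing (R_{AC}), time dependency of the pharmacokinetics". Accumulation "will be calculated as the ratio of the AUC(0-24) on Cycle 2 Day 1 and Cycle 0 Day 1". Time dependency "will be assessed by the calculation of the ratio of AUC(0 -24) Cycle 2 day 1/AUC Cycle 0 Day 1". The trough series is "Trough concentrations on Cycle 1 Day 8, day 15 and Cycle 2 day 1". Section 7.1 lists all of these as primary endpoints.

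**The concern.** The protocol controls clock time within a PK day closely: section 6.5.1 allows 5 minutes around the 1 h sample and 10 minutes from 1.5 to 10 h. It leaves the day of the steady-state profile free over a two-week span. Nothing in sections 5.2, 6.5.1, 7.4 or 7.6 narrows that day. The PK analysis set asks for dosing data on the sample day and the two days before it, but not for a minimum number of daily doses.

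Two patients in the same cohort could therefore contribute AUCss and R_AC values after different lengths of dosing. An early profile may be short of steady state. AUCss and R_AC would then be too low and CLss/F too high. The time-dependency ratio, which is expected to be 1 under linear kinetics at steady state, would fall below 1 merely because accumulation was incomplete. Sites schedule from Table 2, so an analysis plan written later cannot recover the timing.

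**Working it through.** **Reading of the schedule.** As a check that Table 4 is read correctly, count its samples. Cycle 0: 11 on Day 1 plus one each at 24, 48, 72 and 120 h = 15. Cycle 1: 1 on Day 1, 11 on Day 8, 1 on Day 9, 1 on Day 15 = 14. Cycle 2: 9 on Day 1, 1 on Day 2 = 10. The total is 15 + 14 + 10 = 39, and 39 × 2 mL = 78 mL. Both agree with the blood-volume table in section 6.6.1.

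**Alignment of the window row.** Entries 1–5 are Cycle 0 Days 1, 2, 3, 4 and 6 (all 0). Entries 6–9 are Cycle 1 Days 1, 8, 9 and 15 (all 0). Entry 10 is Day 1 of Cycles 2–4 (±7). Entry 11 is Cycle 2 Day 2 (0). Entries 12–14 are Cycle 5 onwards (±7), discontinuation (0) and the 28-day follow-up (±7). Cycle 2 Day 1 is the only PK day without a 0.

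**Day range.** Count multiple-dosing days from Cycle 1 Day 1. Nominal Cycle 2 Day 1 is 1 + 21 = day 22. With ±7 it may fall on day 15 to day 29, that is, after 14 to 28 earlier daily doses (study days 22 to 36).

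**The −7 limit.** Day 15 is Cycle 1 Day 15, a separate trough visit with its own window of 0. The two pre-dose samples would then be the same sample, giving 38 distinct samples instead of 39. Cycle 1 would last 14 days, against the 21-day definition.

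**Size.** The protocol gives no half-life, so a range is assumed. Take a linear one-compartment model with once-daily dosing, rapid absorption and no residue from the Cycle 0 dose. The share of steady-state AUC over the dosing interval on multiple-dosing day n is

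f(n) = 1 − 2^(−24n/t½).

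Example, t½ = 120 h, n = 15: 1 − 2^(−3) = 0.875.

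The accumulation ratio on day n is f(n) / [1 − 2^(−24/t½)]. CLss/F on day n is overstated by 1/f(n) − 1. Under this model the time-dependency ratio equals f(n) itself.

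| Assumed t½ | f, day 15 / 22 / 29 (%) | R_AC, day 15 / 22 / 29 | CLss/F overstated on day 15 |
|---|---|---|---|
| 48 h | 99.4 / 100 / 100 | 3.40 / 3.41 / 3.41 | 0.6% |
| 72 h | 96.9 / 99.4 / 99.9 | 4.70 / 4.82 / 4.84 | 3.2% |
| 96 h | 92.6 / 97.8 / 99.3 | 5.82 / 6.15 / 6.24 | 8.0% |
| 120 h | 87.5 / 95.3 / 98.2 | 6.76 / 7.36 / 7.59 | 14.3% |

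Relative to day 22, the shortfall on day 15 is under 1 percentage point at 48 h, 2.5 at 72 h, 5.2 at 96 h and 7.8 at 120 h. Day 15 reaches at least 95% of steady state when 24 × 15 × ln 2 / (−ln 0.05) ≥ t½, that is, for t½ up to about 83 h.

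**The case against.** The strongest reply is that the loss is small. At 72 h or less, even the earliest permitted visit is within about 3% of steady state, and late visits lie closer to it than the nominal day does. The analysis is descriptive and uses actual sampling times. A site would also have to merge two separately listed visits to reach the −7 limit. All of this stands and keeps the point modest. Actual sampling times, however, correct the clock within the profile and not the number of doses before it.

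It could also be said that the 0 on Cycle 2 Day 2 pins Day 1 to day 22. But the Day 2 sample is the 24 h sample of the Day 1 dose, with a 1 h window, so it moves with Day 1. If its 0 is instead counted from the nominal calendar, it contradicts the ±7 beside it.

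Three stronger readings are tempting and are not supported:

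- **A late visit follows a gap in supply.** A reader might infer that a day-29 patient has run out of the drug dispensed at Cycle 1 Day 1. Table 2 also dispenses at Cycle 0 Day 1, and section 5.2 says "At each dispensing visit, sufficient AZD9291 for 21 days treatment, plus overage, will be dispensed". Cycle 0 uses one dose, so on a literal reading 20 daily doses remain from the first supply and 21 come with the second, before any overage. Section 5.2.5 asks for return of unused drug but does not say when. Doses missed around PK sampling are also dealt with: section 5.2 calls for advice on evaluability and PK timing after missed doses in Cycle 1, section 6.5.1 calls for discussion if dosing is interrupted within 3 days of sampling, and section 7.6 excludes important deviations that may affect PK.
- **The troughs can no longer show steady state.** Even at the −7 limit, pre-dose values remain on Cycle 1 Days 8, 9 and 15 and on Cycle 2 Day 2. The synopsis counts the 24 h value of Cycle 2 Day 1 as a trough. The series is weakened, not lost.
- **Cycle 1 Day 8 supplies no full profile.** It does: 12 samples including Day 9, against 10 in Cycle 2. But the protocol does not label it steady state and derives neither AUCss, CLss/F, R_AC nor time dependency from it.

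**Conclusion.** The point holds as an inconsistency in Table 2 that is worth correcting. The one visit that carries the labelled steady-state parameters, accumulation and time dependency has a two-week span, while every other PK day is fixed, and no other section narrows it. The early limit also collides with the Cycle 1 Day 15 visit and with the 21-day cycle.

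The size depends on a half-life that the protocol does not give and on an assumed linear one-compartment model. Over 48 to 120 h, the early-visit shortfall relative to day 22 runs from under 1 to about 8 percentage points of steady-state AUC. It is negligible at short half-lives. It matters only if the parent or a metabolite has a long half-life, or if kinetics change with time, which the study itself sets out to assess. The plan's PK analysis is not invalid because of it.

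**What to change.** In Table 2, separate Cycle 2 Day 1 from the Day 1 column of Cycles 3 and 4. Give it the 0-day window of the other PK visits, or at most ±1 day, and keep ±7 days from Cycle 3 onwards. With a window of 0, every patient's profile falls on multiple-dosing day 22. State that the Cycle 2 Day 2 window is counted from the Cycle 2 Day 1 dose.

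The cost is less scheduling flexibility for one visit per patient. A rule that drops out-of-window profiles from the summaries is not recommended: with about 12 patients per cohort it would discard primary data, including late profiles that lie nearer to steady state.
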